YT	YouTHrive

STUDY ABSTRACT

DESIGN:	
YouTHrive (YT) is a two-arm randomized controlled trial (RCT) to test the efficacy of an adapted version of the Thrive With Me intervention for youth living with HIV (YLWH).

DURATION:	YLWH are enrolled for 5 months.
SAMPLE SIZE:	Total study sample is 368 of which the following will be enrolled for each aim: 1) 48 participants for focus groups to inform intervention adaption; 2) 12-20 participants for usability testing to finalize intervention components; 3) 300 participants for a randomized controlled trial of YT, with participants randomized to either YT (n=150) or control (n=150).
POPULATION:	Participants for all aims of the study will include YLWH inclusive of all genders and all races/ethnicities. Focus group participants will be recruited from SRVs in Bronx, Chicago, and Houston. Usability participants will be recruited from SRVs in Bronx, Chicago, Houston, Philadelphia, Tampa, and Atlanta. RCT participants will be recruited from SRVs in Bronx, Chicago, Houston, Philadelphia, Tampa, Atlanta, Raleigh/Durham/Chapel Hill and Charlotte area. Usability participants must have had a detectable VL in the past 12 months. RCT participants will be required to meet eligibility criteria.
STRATIFICATION:	Focus group discussions will be stratified by age (50% 15-19 yo; 50% 20-24 yo). We will stratify by SRV (i.e., city) site for the RCT.
DATA COLLECTION:	Focus group discussions will be conducted in-person, digitally recorded, and professionally transcribed. There will be three data collection (screening, baseline, and 5-month) time points for the RCT. Visits are conducted in-person at the SRV or remotely. Surveys will be completed using online survey tools (Alchemer and Qualtrics). VL measure collection will occur in-person at the participant's SRV or remotely. Urine screen will happen at in-person visits only. Process data of participant activity on YT and control interventions will include log-in activity, tasks completed on the website, and number of written posts.

OBJECTIVES:

- 1) In a 2-arm RCT (n=300), assess the efficacy of YouTHrive (YT) to sustain suppressed viral load (VL) among YLWH, compared to an HIV information-only control condition.
- 2) Assess whether YT is more beneficial for substance-using than non-substance-using YLWH.

INTRODUCTION

1.1 Background

Fifty thousand persons are estimated to be infected with HIV in the United States each year,¹ of whom one-quarter were youth between the ages of 13 and 24 years in 2010.² Young gay and bisexual men accounted for 72% of all new HIV infections in the same year, with the majority of those being black youth.² Despite elevated risk for HIV infection, it is estimated that only 6-16% of youth/young adults living with HIV (YLWH) are virally suppressed.³⁻⁵ Sufficient and sustained adherence to antiretroviral therapy (ART) reduces excess morbidity and mortality among people living with HIV (PLWH)⁶ and lowers the probability of forward transmission to sexual partners.⁷ Advancing targeted and innovative ART adherence interventions for YLWH is an urgent priority.³

Technology-supported ART adherence interventions have proliferated in recent years⁸⁻¹⁰ due to the widespread adoption of technology across sociodemographic groups,¹¹ their ability to reach a broad audience, rapid scalability, and low implementation costs.^{12,13} In the US, nearly all teens (between 12-17 years of age) use the Internet¹⁴ and 78% own a cell phone.¹⁵ Smartphone ownership among 18-29 year olds is high (86%).¹⁶ ART adherence interventions that leverage software on PCs or through the internet¹⁰ capitalize on consistency in delivery of content and long-term cost savings; however, to date the peer-to-peer interactivity that has come to symbolize Web 2.0¹⁷ remains underutilized in technology-based ART adherence approaches. Peer-to-peer support is a recommended strategy to improve ART adherence,¹⁸ is widely used by PLWH,¹⁹ and has an evidence-base for in-person approaches (especially with adults²⁰). However, youth in the US are increasingly accustomed to technology-mediated peer-to-peer interactions, suggesting that intervention approaches that specifically leverage high-use channels of interpersonal communication and support are needed.

The “Thrive with Me” (*TWM*) intervention leverages enhanced peer-to-peer interaction, ART adherence reminders and self-monitoring, and ART and HIV informational content²¹ to improve ART adherence. In a pilot study of 123 adult MSM (average age = 43 years), those randomized to the *TWM* intervention showed improvements across all ART adherence outcomes compared to control participants, with greatest benefits for current drug-using MSM. Currently, our research team is funded to conduct an efficacy trial of an extended (5-month intervention period) and enhanced (tailored informational content; multi-dimensional self-monitoring; and gamification components, such as leveling and badges) version of the *TWM* intervention for adult MSM. Given youth’s broad acceptance and adoption of many of the components of the *TWM* intervention, and the critical need for novel and scalable ART adherence interventions for this population, the next logical step is to adapt the *TWM* intervention for YLWH.

As part of the UNC/Emory Center for Innovative Technology (iTech), we propose to test the efficacy of an adapted version of the *TWM* intervention, called YouT^Hrive (YT), for YLWH. In this 4-year study, 300 YLWH between the ages of 15-24 with detectable viral load (VL) will be randomized to the YT or an HIV information-only control intervention for a 5-month period. A target of 50% of YLWH participants with self-reported alcohol and/or illicit drug use will be enrolled. The primary endpoint is VL post-intervention.

1.2 Rationale

There is a clear need to develop effective ART adherence interventions that meet the needs of YLWH. Although young MSM – especially racial and ethnic minorities – are at high risk for acquiring HIV and, if HIV-positive, having poor ART adherence, relatively few ART adherence interventions exist that are tailored to the needs of this population. For this reason, The *TWM* online peer-to-peer support intervention will be adapted for YLWH and assessed for effectiveness in a 2-arm randomized controlled trial (RCT) called YouT^Hrive (YT).

1.2.1 Focus groups with youth (ages 15-19 years old) and young adults (20-24 years old)

Focus groups will provide insights into what features and functions of the current TWM study youth like and dislike to assist intervention adaptation. Focus groups will be conducted at 3 SRVs (Bronx, Chicago, and Houston), and stratified by age (15-19 years old & 20-24 years old), to ensure that a geographically and demographically diverse sample of youth and young adults provide input to guide intervention adaptation. In addition, age stratification is intended to help younger participants (15-19 years old) to feel more comfortable sharing their opinions and feedback.

1.2.2 Usability Testing

The purpose of usability testing is to gain feedback about the intervention once a functional version of the intervention is available and to give SRV staff experience in implementing all procedures associated with intervention arm participation. It is primarily intended to get feedback from the target population about any technical issues they encountered, as well as to obtain any feedback about the look and feel of *YT*. As we have done in prior technology-based studies, we will recruit up to 12-20 youth total across the 6 SRVs where the RCT will occur: Houston, Bronx, Chicago, Tampa, Atlanta, and Philadelphia to use the *YT* intervention for a 2-week period. In order to ensure diversity in the sample, each SRV site will recruit two total participants, one male and one female from the younger (15-19 years old) and older (20-24 years old) age categories. We also will recruit at least one perinatally infected female, one perinatally infected male, and at least one behaviorally infected gay or bisexual male (these targets will be across all sites, not per site). SRV research staff will briefly introduce participants to the intervention and provide instruction on how to log their impressions and feedback about the intervention. After the 2-week period, participants will participate in an online interview using VSee to interact with *YT* research staff to provide their feedback about *YT*. The information will be placed in summary form, and provided to our technology development partner to guide any final changes to the *YT* intervention.

1.2.3 RCT of *YT*

A 2-arm RCT of *YT* will be conducted, comparing the full version of the *YT* intervention to a control group. The control group will consist of weekly e-mails with a link to a webpage containing information about topics of interest to YLWH, but not addressing ART adherence. A RCT was chosen since it is the gold standard for assessing the effectiveness of an intervention under tightly controlled conditions. The intervention and control group will have access to intervention content for 5 months, with CASI performed at baseline and 5-month (i.e., immediate post intervention). VL will be assessed at baseline and 5- month time points to assess primary hypotheses (i.e., more participants in the *YT* group will have undetectable VL at the 5-month and assessment and, among those in *YT*, a greater proportion of substance-using participants will demonstrate sustained virally suppression than non-substance-using participants). Up to twenty purposively selected participants from the intervention group will also take part in a short, semi-structured interview over VSee or Zoom about their experiences on the site with study staff at their 5-month follow-up.

STUDY OBJECTIVES

2.1 **Primary Objective:** In a 2-arm RCT ($n=300$), assess the efficacy of YouT^hrive (*YT*) to sustain suppressed viral load (VL) among YLWH, compared to an HIV information-only control condition.

2.2 **Secondary Objective:** Assess whether YT is more beneficial for substance-using than non-substance-using YLWH.

2.3 Study Hypotheses/Research Questions

- *H1: A higher proportion of participants in the YT intervention arm than in the information-only control arm will have undetectable VL at the 5-month follow-up time point.*
- *H2: Among YLWH in the YT intervention arm, a higher proportion of substance-using YLWH will demonstrate VL suppression at the 5-month follow-up time point compared to non-substance-using YLWH.*

STUDY DESIGN

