10.3.4 Secondary Analyses for RCT of YouTHrive

As a secondary aim, we will investigate whether there is greater benefit from the YT intervention for substance-using participants compared with nonsubstance-using participants. We will use the same modeling approach described above to address this aim. First, we will examine the association between the intervention and viral detection separately among those who did and did not self-report current (since the last visit) substance use (i.e., yes/no for problematic alcohol use and/or illicit drug use). Second, to formally test whether there is an interaction between intervention arm and substance use, the models described above will be refit including an interaction term between substance use and intervention arm. Interactions will be evaluated on the additive scale. We will carefully examine the distribution of potential confounders of the substance use and VL association and adjust for them as necessary. As mentioned previously, we will adjust for covariates where appropriate.

The models described use logistic regression to model the outcomes. We will use estimates from these models to report prevalence differences and ratios. However, alternative (log-linear and Poisson) models may be explored to allow easy interpretation of parameters in the presence of common outcomes. In the event of loss-to-follow-up among study participants, we will perform sensitivity analyses of an alternative outcome. We will define an additional outcome where a failure is defined as either detectable VL or loss-to-follow-up. The analyses described above will be repeated with this alternative outcome. All of the models mentioned above can be modified to accommodate missing values in the outcome or covariates over time without dropping participants. Although attempts will be made to limit missing data, in the event that this occurs, we will carefully examine patterns of missingness. Multiple imputation will be implemented, as needed, to deal with missing covariate data.

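### H2 compares substance users with non-users inside the YT arm only, so it does not answer objective 2.2 or match the interaction planned in 10.3.4, whose moderator is tied to no named visit

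*Combined protocol and SAP*

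**What the plan says.** Objective 2.2, the secondary objective, is to "Assess whether YT is more beneficial for substance-using than non-substance-using YLWH".

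H2 in section 2.3 reads "Among YLWH in the YT intervention arm, a higher proportion of substance-using YLWH will demonstrate VL suppression" at 5 months than non-users. Section 1.2.3 repeats the contrast for the YT arm, "a greater proportion of substance-using participants will demonstrate sustained virally suppression than non-substance-using participants", and introduces it with "time points to assess primary hypotheses", although 2.2 and 10.3.4 treat the question as secondary.

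Section 10.3.4 plans something different, in two steps. The arm effect is first examined separately in "those who did and did not self-report current (since the last visit) substance use". The models are then refitted with a product term "to formally test whether there is an interaction between intervention arm and substance use", judged on the additive scale. No visit is named for the substance-use report.

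Other sections bear on that report:
- The Study Abstract lists three RCT time points: screening, baseline and 5 months.
- Section 5.1 allows up to 60 days from screening to enrolment, and 3.1 lets both happen in one visit.
- Section 6.3 accepts the 5-month assessment from 30 days early to 60 days late.
- Section 3.2 sets a 50% enrolment target for substance use with the same two components (alcohol and drugs) but a past-6-months window.
- Sections 3.1 and 3.3.3 randomise at the outset of the survey; 5.1 and 5.3 randomise after it.

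**The concern.** Benefit from YT means YT against control, so objective 2.2 concerns a difference between two arm effects. H2 has no control comparator. Users and non-users differ in ways that randomisation does not balance, and 10.3.4 itself refers to confounding of the association between substance use and viral load. A report that answered H2 literally could claim extra benefit for users where YT had none, or miss it where it existed. Hypothesis and planned test could also point in opposite directions, leaving room to choose between them after seeing the data.

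The moderator matters because the correct interaction test depends on it. If it is not tied to a visit, the subgroups are open to choice, and under one reading they form after randomisation.

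**Working it through.** **Inputs.** Section 10.2.3 bases power on 240 participants with equal allocation, so 120 per arm. Section 3.2 targets 50% users, giving 60 per arm-by-use cell. The plan states no suppression rates for these cells and no power for H2 or the interaction, so every rate below is assumed, including which group does better.

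**The plan's own figure.** The detectable adherence difference in 10.2.3 is (1.960 + 0.842) × 43 × √(2/120) = 15.55 points (15.62 by the t distribution), against 15.6 stated. It reproduces at 120 per arm with two-sided 5%, the convention used below.

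**Identity.** Let Y and C be the suppression proportions under YT and control, with u for users and n for non-users:

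Y_u − Y_n = [(Y_u − C_u) − (Y_n − C_n)] + (C_u − C_n)

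The left side is H2. The bracket is the additive interaction, which answers objective 2.2. The last term is the gap under control, which YT cannot affect. This needs no assumed rates.

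**H2 true, YT inert.** Take 60% (users) and 50% (non-users) in both arms.
- H2 contrast: 0.60 − 0.50 = +0.10. Interaction: 0 − 0 = 0.
- SE = √(0.60×0.40/60 + 0.50×0.50/60) = 0.0904; z = 0.10/0.0904 = 1.107.
- Probability of significance in H2's direction: Φ(1.107 − 1.960) = 0.197.
- With 60%/40% in both arms: SE 0.0894, z = 2.236, probability 0.609.
- With 64 per cell (85% of 300 = 255; 255/4 ≈ 64), the two probabilities are 0.207 and 0.637.

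**H2 false, users benefit more.** Take control 40%/60% and YT 58%/62% (users/non-users).
- Interaction: (0.58 − 0.40) − (0.62 − 0.60) = +0.16.
- H2 contrast: 0.58 − 0.62 = −0.04, SE 0.0894, 95% CI −0.215 to +0.135.
- Check: 0.16 + (0.40 − 0.60) = −0.04.

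**Moderator read at 5 months.** The window since enrolment is about 4 to 7 months, all after randomisation. At the stated 85% follow-up, 300 × 0.15 = 45 participants would have no report. The sensitivity analysis "where a failure is defined as either detectable VL or loss-to-follow-up" keeps these participants in the outcome but cannot place them in a subgroup without further rules.

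To size the bias, assume half are users; control suppression is 35% in those who use regardless of arm and 60% in non-users; YT adds 10 points for everyone; and YT moves 5% to 15% of the sample from user to non-user. If the movers' control rate is 55%, the false interaction is −1.5 to −4.8 points. If it is 45%, it is about +0.4 to +0.5. The interaction SE is √(4p(1−p)/60): 0.092 at p = 0.85, 0.118 at 0.30 and 0.129 at 0.50. The bias is small beside it.

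**Moderator read at baseline.** The window is the time since screening: at most 60 days, and empty if screening and enrolment share a visit.

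**Power of the correct test.** Detectable interaction at 80% power = 2.802 × √(4p(1−p)/60): 33.1 points at p = 0.30, 36.2 at 0.50 and 35.4 at 0.60.

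**The case against.** The strongest reply is that 10.3.4 already contains the right analysis. That stands. A reader might infer from the 0.20 and 0.61 figures that the trial will run a test with inflated error. The documents do not support this: section 10.3 plans no test of H2 as worded, and the figures show only what would happen if someone ran one. They also require users to do better than non-users under control, and nothing in the documents says so. Section 10.3.4 does plan confounder adjustment; this tempers a user v non-user comparison but supplies no control comparator.

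Three stronger readings of the moderator problem also fail:
- One might take 300 − 240 = 60 as the number lost. Section 10.2.3 never says that the 240 are what remains of 300; only 45 follows from the stated rate.
- One might say a 5-month moderator would have to be imputed. Section 10.3.4 says "Multiple imputation will be implemented, as needed, to deal with missing covariate data", and 10.4 allows complete-case analysis when few cases are missing.
- One might say substance use is undefined throughout the study. The Schedule of Evaluations is not in the text available, so the point is confined to the wording of 10.3.4.

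It is also fair that screening may be an online survey (4.5) and so may not count as a visit. That weakens the baseline reading, but it leaves the post-randomisation reading as the natural one.

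**Conclusion.** The point holds as a mismatch between objective, hypothesis and planned analysis, together with a moderator whose visit is not named. The identity is exact: H2 carries the control-arm gap in full. Under the assumed 60%/50% rates, H2 shows +10 points with zero interaction; under the reverse example, it shows −4 with an interaction of +16. How far H2 would mislead here depends on a gap the documents do not give.

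The moderator wording should be fixed because it leaves the subgroups open, rather than because of a large bias: under the 5-month reading the illustrated bias is at most about 5 points, against an SE of 9 to 13. The effect is limited to the secondary objective. A reader might infer that the primary efficacy result is at risk; it is not, since the two-arm comparison in 10.3.3 uses neither H2 nor the moderator.

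**What to change.** 1. Reword H2 in 2.3, and the matching clause in 1.2.3, as: *the YT-minus-control difference in the proportion with undetectable VL at 5 months is larger among baseline substance users than among baseline non-users*. Label it secondary in both places and tie it to the additive-scale interaction in 10.3.4. No new analysis is needed.
2. In 10.3.4, replace the since-last-visit definition with self-reported problematic alcohol and/or illicit drug use in the past 6 months (the window in 3.2), taken from the screener or the baseline CASI and recorded before randomisation.
3. Reconcile 3.1 and 3.3.3 with 5.1 and 5.3 on when randomisation happens. If assignment comes at the survey outset, baseline CASI answers follow it and item 2 is not met from that source.

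**Cost.** Mostly wording, but item 2 fixes a pre-specified analysis variable. The team must confirm that the screener or baseline CASI records this window; the target in 3.2 suggests so but names no instrument. The moderator will then describe use before the intervention, not during it. Power for the interaction is low: about 33 to 36 points detectable with 60 per cell at suppression of 30% to 60%, against about 23 to 26 for the within-YT contrast (2.802 × √(2p(1−p)/60)). That contrast is more precise, but it answers a different question.

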3.1 Study Phases/Aims

We will evaluate the *YT* intervention in a randomized controlled efficacy trial (see *YT* Schema) YLWH will be recruited from the 8 SRVs (Bronx, Houston, Chicago, Philadelphia, Tampa, Atlanta, Raleigh/Durham/Chapel Hill, and Charlotte), screened, and randomized to receive either the *YT* intervention or HIV-information only control condition. VL will be collected at the enrollment visit and 5-month follow-up assessment time point.

Phase/Aim 1: YT Intervention Adaptation

We will conduct six focus groups with approximately 8 youth (15-19 years old) and young adults (20-24 years old) each at 3 SRVs to obtain: 1) feedback from YLWH about the “look and feel” and content of the original *TWM* intervention; 2) suggestions for adapting the intervention for YLWH similar to themselves; 3) information about barriers to ART adherence and other challenges of living with HIV. Focus groups will be transcribed verbatim and a content analysis will be assisted by the Analytic Core (AC).

Phase/Aim 2: YT Adaptation and Build

Information and feedback gathered from the focus groups will inform the adaptation of the *TWM* intervention for YLWH. The ADAPT-ITT model will be used to guide the adaptation process. Briefly, the ADAPT-ITT model follows 8 steps- each contributing to the acronym; **A**sessment of target population needs and local resources; **D**ecision making on components to leverage and adapt from *TWM*; **A**daptation of components to target group and pre-testing; **P**roduction of intervention draft; **T**opical experts review adaptations; **I**ntegration of feedback leading to second draft; **T**raining for implementation; and **T**esting.

[name] and the research team will partner with Radiant Creative Group (RCG) in order to update the *TWM* intervention to include those features and functionality that arise during the aforementioned adaptation process. Usability testing with 12-20 participants at 6 SRVs (Bronx, Chicago, Houston, Philadelphia, Tampa, and Atlanta) will be conducted to finalize all features and components of the intervention (i.e., ensure that all features are working properly and function in a way that users can easily navigate).

Phase/Aim 3: Randomized Controlled Trial to Test Efficacy of YT

YLWH will be recruited from 8 SRVs (Bronx, Houston, Chicago, Philadelphia, Tampa, Atlanta, Raleigh/Durham/Chapel Hill, and Charlotte). Persons interested in the study will be screened to determine if they meet the eligibility criteria. Prospective participants can screen remotely or in person, and can be recruited within the SRV clinic or in the community, as long as they meet inclusion criteria. YLWH who meet all inclusion criteria will be invited for either an in-person or virtual enrollment visit. Screening and enrollment may also happen during one visit, when possible.

At the enrollment visit, participants will complete an in-office or online baseline CASI, complete a viral load test if one was not performed in the past 60 days, a urine screen for recent drug use, and will be randomized at survey outset to either intervention or control. The randomization sequence will be stratified by city and use random permuted blocks of size 2 and 4. YLWH assigned to the *YT* intervention will be shown example webpages of the intervention, will be given basic training on how to navigate the intervention, and will be given the opportunity to ask questions they have about the website. Control condition assigned participants will be shown example webpages they will receive during the intervention period.

The intervention period lasts five months. During this time, intervention participants will have continuous access to the *YT* website (mobile enhanced and available on all devices with internet connection). Participants in the control condition will receive an email with HIV-related information once per week.

Follow-up assessments will be conducted at the 5-month (i.e., immediate post-intervention; follow-up 1 in the clinical setting or online via a teleconferencing platform such as VSee or Zoom) time point. The 5-month follow-up visit will include an in-office or online administered CASI, a blood draw or self-administered finger prick to test for detectable viral load, and a urine screen for drug use. At the 5-month follow-up visit, up to 20 intervention participants will be offered additional compensation (as specified in each SRV's informed assent/consent form) to take part in an additional semi-structured interview with SRV staff or via Zoom with a member of the study team.

